MRI	Magnetic Resonance Imaging
mRS	Modified Rankin Scale
NIHSS	National Institute of Health Stroke Scale
OLVG West	Onze Lieve Vrouwe Gasthuis, locatie Amsterdam West
SAE	Serious adverse event
Sponsor	The sponsor is the party that commissions the organisation or performance of the research, for example a pharmaceutical company, academic hospital, scientific organisation or investigator. A party that provides funding for a study but does not commission it is not regarded as the sponsor, but referred to as a subsidising party.
VUMC	Vrije Universiteit Medisch Centrum, 1 of 2 Amsterdam UMC locations
WMO	Medical Research Involving Human Subjects Act (in Dutch: Wet Medisch-wetenschappelijk onderzoek met mensen)

SUMMARY

RATIONALE

Endovascular thrombectomy (EVT) is standard treatment for acute ischemic stroke (AIS) if there is a large vessel occlusion in the anterior circulation (LVO-a). Because of its complexity, EVT is performed in selected hospitals only. Currently, approximately half of EVT eligible patients are initially admitted to hospitals that do not provide this therapy. This delays initiation of treatment by approximately an hour, which decreases the chance of a good clinical outcome. Direct presentation of all patients with a suspected AIS in EVT capable hospitals is not feasible, since only approximately 7% of these patients are eligible for EVT. Therefore, an advanced triage method that reliably identifies patients with an LVO-a in the ambulance is necessary. Electroencephalography (EEG) may be suitable for this purpose, as preliminary studies suggest that slow EEG activity in the delta frequency range correlates with lesion location on cerebral imaging. Use of dry electrode EEG caps will enable relatively unexperienced paramedics to perform a reliable measurement without the EEG preparation time associated with 'wet' EEGs. Combined with algorithms for automated signal analysis, we expect the time of EEG recording and analysis to eventually be below five minutes, which would make stroke triage in the ambulance by EEG logically feasible.

HYPOTHESIS

We hypothesize that dry electrode cap EEG can be used in patients with a suspected AIS to identify patients with an LVO-a in the ambulance.

OBJECTIVE

To determine the diagnostic accuracy of dry electrode cap EEG for diagnosis of LVO-a, when performed by paramedics in the ambulance in patients with a suspected AIS.

STUDY DESIGN

This diagnostic study consists of four phases:

Phase 1: Optimization of measurement time and software settings of the dry electrode cap EEG in a non-emergency setting in patients in whom a regular EEG is/will be performed for standard medical care.

Phase 2: Optimization of measurement time and software settings of the dry electrode cap EEG in patients close to our target population in a non-emergency setting.

Phase 3: Validation of several existing algorithms and development of one or more new algorithms for LVO-a detection, as well as optimization of logistics and software settings of the dry electrode EEG cap in patients close to our target population in an in-hospital emergency setting.

Phase 4: Validation of several existing algorithms and algorithms developed in phase 3 for LVO-a detection in patients with a suspected AIS in the ambulance, as well as assessment of technical and logistical feasibility of performing EEG with dry electrode caps in patients with a suspected AIS in the ambulance.

STUDY POPULATION

Phase 1: Patients in the outpatient clinic of the Clinical Neurophysiology department of the AMC, in whom a regular EEG has been/will be performed for standard medical care.

Phase 2: Patients with an AIS admitted to the Neurology ward of the coordinating hospital with an LVO-a (after reperfusion therapy).

Phase 3: Patients with a suspected AIS in the emergency room (ER) of the coordinating hospital (before reperfusion therapy).

Phase 4: Patients with a suspected AIS in the ambulance.

INTERVENTION

Performing a dry electrode cap EEG (in phase 1 in the outpatient clinic, in phase 2 during hospital admission, in phase 3 in the ER and in phase 4 in the ambulance).

MAIN END POINTS

- Primary end point: the area under the receiver operating characteristics (ROC) curve of the theta/alpha ratio for diagnosis of LVO-a, based on dry electrode EEG performed by paramedics in the ambulance in suspected AIS patients;
- Secondary end points:

- Sensitivity, specificity, positive predictive value (PPV) and negative predictive value (NPV) of the theta/alpha ratio, and test characteristics of other existing EEG data based algorithms for LVO-a detection (e.g. Weighted Phase Lag Index, delta/alpha ratio);
- Logistical and technical feasibility of paramedics performing dry electrode cap EEG in the ambulance in suspected AIS patients ;
- Developing one or more novel EEG data based algorithms with optimal diagnostic accuracy for LVO-a detection in suspected AIS patients with ambulant dry electrode cap EEG.

NATURE AND EXTENT OF THE BURDEN AND RISKS ASSOCIATED WITH PARTICIPATION, BENEFIT AND GROUP RELATEDNESS

A single EEG is performed on each patient. The EEG is a safe, non-invasive and painless procedure that is used regularly in standard medical practice. It does not involve electromagnetic radiation. The use of dry electrodes makes the procedure less time-consuming. After optimization of measurement time in phase 1 and 2, the procedure will take less than five minutes in total. Therefore, when the measurements are performed in an emergency setting in phases 3 and 4, the procedure can be completed within the time it takes the treating physician or paramedic to perform their regular work-up. This way, initiation of treatment will not be delayed. We expect the dry electrode cap to cause no to minimal discomfort, and only during the measurement. We will use CE marked products for performing the dry electrode cap EEGs. The results of the EEG will only be analyzed after admission or discharge, and will therefore not influence the choice of hospital by the paramedic. As soon as feasible, preferably within 72 hours after arrival at the hospital or at discharge (whichever comes first), deferred informed consent will be asked. If informed consent is given, a CRF will be filled out containing information on patient characteristics, medical history, medication use, physical and neurological examination performed by the treating physician, results of imaging studies, diagnosis and treatment as well as logistical and technical information, obtained from the patient, the treating physician and the ambulance service. There are no follow up visits. For the patient, there is no benefit of participation in the study.

1. INTRODUCTION AND RATIONALE

Acute ischemic stroke (AIS) is a major cause of mortality and morbidity worldwide, affecting approximately 1 per 1000 people per year¹. In the Netherlands, 20.000 people are hospitalized with AIS each year, of whom 25-30% die because of the stroke^{2,3}. Since the 1990's, intravenous thrombolysis (IVT) has been standard treatment for AIS⁴. In 2015, there was a breakthrough in treatment of AIS with the publication of 5 large randomized controlled trials showing the effectiveness of endovascular thrombectomy (EVT) in patients with a large vessel occlusion in the anterior circulation (LVO-a)⁵. Since then, EVT has been become standard therapy for this population until 6 hours after stroke onset, and as of recently, for a selected population, up to 24 hours⁵⁻⁷. It is important to initiate treatment as soon as possible, as this increases the chance of a good clinical outcome⁸.

Because of its complexity, EVT is performed only in selected hospitals. Currently, approximately half of EVT eligible patients are initially admitted to a hospital that does not provide this therapy. After the initial work-up, these patients are transferred to an EVT capable hospital. This delays initiation of treatment by approximately an hour, which decreases the absolute chance of functional independence 3 months after the stroke by 5-8%^{8,9}. An advanced triage method that reliably identifies patients with an LVO-a in the ambulance is necessary, so that these patients can be directly transported to an EVT capable stroke center.

A triage method for this purpose needs to have both high specificity and high sensitivity for LVO-a. The sensitivity of the diagnostic method is important, because a false negative test result means that the patient would be transported to a non EVT capable hospital, delaying his/her treatment. However, we deem the specificity of the method even more important, for the following reasons. Currently, EVT capable hospitals are overburdened because many patients with a suspected stroke are directly brought to these hospitals, as paramedics often do not want to take the chance of bringing a patient to the 'wrong' hospital. However, only a small part of these patients, circa 7%, is eligible for EVT. This causes EVT capable hospitals to have low capacity for admission of patients that do need specialized care. Additionally, patients with expected stroke currently are first evaluated in the emergency room where they undergo diagnostic procedures, and are then brought to the angiography room to undergo EVT. This takes approximately an hour from entering the hospital to the start of treatment (not all this time is due to diagnostic procedures, but also to other logistical issues that are not addressed in this study). Currently, the angiography room is not being prepared for every patient that is presented to the

emergency room with a suspected stroke, because of the low a priori chance of eligibility for EVT in patients with a suspected stroke. A diagnostic method with high specificity will make it possible, in patients in whom a high likelihood of an LVO-a has been determined in the ambulance, to minimize (or maybe even leave out) diagnostic procedures in the emergency room and to present these patients directly to the angiography room, in order to save time. Several methods for determining the likelihood of an AIS with an LVO-a have been proposed. However, none of these have been found to be suitable for prehospital triage. Clinical scales, containing items for scoring the severity of neurological deficit, are difficult to be reliably applied by paramedics and have low diagnostic accuracy¹⁰. Another option for pre-hospital stroke triage that has been explored, is equipping ambulances with an imaging system for performing non-contrast CT and CT angiography to diagnose LVO-a and, in some studies, give IVT. However, its efficacy has not been proven and there are concerns regarding the safety and cost-effectiveness of this method¹¹. An effective and safe prehospital triage method for stroke that can be reliably performed and analyzed by paramedics has not yet been found.

Electroencephalography (EEG) may be suitable for prehospital triage, as preliminary studies suggest that slow EEG activity in the delta frequency range correlates with lesion location on cerebral imaging^{12,13}. Another study has suggested using (a)symmetry in brain activity for monitoring of stroke patients¹⁴. EEG is already being used in clinical practice for monitoring for signs of cerebral ischemia during carotid surgery while the carotid artery is clamped, and can predict the likelihood of postoperative neurological deficit with high specificity (84-92%)^{15,16}. This suggests that the occlusion of a large artery, similar to clamping of the carotid artery in its effect on cerebral blood supply, could also be predicted by EEG. One case-control study found that in patients with a recent AIS, the Brain Symmetry Index – an index that expresses EEG asymmetry (the higher the index, the more asymmetrical is the EEG signal) – positively correlated with severity of neurological deficits¹⁷. Other case-control studies have shown that ratios between slow and fast EEG activity, such as the delta/alpha ratio, can be used to discriminate between AIS patients and healthy controls with high sensitivity and specificity^{18,19}. The Weighted Phase Lag Index, a measure for functional connectivity between different areas of the brain, has also been proposed for this purpose¹⁹. Although a regular EEG measurement takes approximately an hour, mostly due to preparation time, using dry electrode EEG caps decreases preparation time dramatically²⁰. Combined with algorithms for automated signal analysis, we expect the time of a single EEG recording and analysis to be below 5 minutes, which will make stroke triage in the ambulance by EEG logistically feasible. Automated analysis would make it unnecessary for paramedics to be schooled in EEG interpretation;

combined with the easily applicable dry electrode cap, this should enable relatively unexperienced paramedics to perform a reliable measurement.

To our knowledge, no study of the diagnostic accuracy of EEG for LVO-a has been performed. We hypothesize that EEG can accurately predict the likelihood of the presence or absence of an LVO-a in patients with a suspected AIS when performed in the ambulance by paramedics. If this is indeed true, then EEG could be used for triage for patients with a suspected AIS, in a similar way the electrocardiography (ECG) is currently used for triage in patients with suspected myocardial infarction in the ambulance: by bringing patients with a high likelihood of necessity of endovascular therapy directly to an EVT capable center.

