For study phase 4, where we aim to validate existing algorithms and one or more new algorithms for LVO-a detection, our primary outcome measure is the specificity of the dry electrode cap EEG in a population of patients with a suspected AIS. Sample size calculation is based on an expected specificity of 70% for LVO-a. Originally, sample size calculation was based on an expected LVO-a rate of 7% and a dropout rate of 20%. However, an interim analysis, based on 137 suspected stroke patients in whom an EEG was performed in the ambulance, showed an actual incidence of LVO-a of 5% and a dropout rate of 58%. Patients considered as a 'drop out' had insufficient EEG data quality (n=72), onset of symptoms >24 hours before EEG registration (n=4) or did not give consent for participation in the study (n=3). The EEG data quality increased over the course of the study, so we expect a lower dropout rate for future EEG registrations. Based on these interim data, we adjusted the sample size for phase 4 of the study as follows.

With an incidence of LVO-a of 5% among patients with a clinically suspected AIS in the ambulance, an alpha of 0.05, and a maximum margin of error of 7%, 174 patients with a suspected AIS are required²¹. Assuming a dropout rate of 55%, we intend to recruit 386 patients with a suspected AIS. A patient is considered a 'drop out' if no informed consent is/can be obtained, if no information on the diagnosis made by the treating physician is/can be obtained, or if the EEG measurement is of insufficient technical quality, as judged by the clinical neurophysiologist. Patients included in the 'run in' phase are excluded from the primary analysis and thus not included in our sample size calculation. In the 'run in' phase, we will additionally include 50 patients or less.

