8. METHODS

8.1 STUDY PARAMETERS/END POINTS

8.1.1 MAIN STUDY PARAMETER/END POINT

The primary end point of the study is the area under the ROC curve of the theta/alpha ratio for diagnosis of LVO-a, based on dry electrode EEG performed by paramedics in the ambulance in suspected AIS patients.

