10. STATISTICAL ANALYSIS AND ALGORITHM DEVELOPMENT

STUDY PHASE 1 AND 2

For phase 1 and 2 of this study, the obtained data will not be statistically analyzed, for these phases are meant to gain technical and logistical information on the products being used in a non-emergency setting.

STUDY PHASE 3

For phase 3 of this study, we will determine the diagnostic accuracy of several existing and one or more self-developed EEG data based algorithms for LVO-a detection by comparing the proportions of patients with and without an LVO-a as predicted by EEG to the proportion of patients with and without an LVO-a as diagnosed by the treating physician. A receiver operating characteristic (ROC) curve will be plotted for each algorithm and the optimal cut-off value for each algorithm will be determined. For these cut off values, the sensitivity, specificity, negative predictive value and positive predictive value will be reported with 95% confidence intervals.

ALGORITHM DEVELOPMENT

Data of phase 3 and phase 4 will be used to develop one or more new EEG based algorithms for LVO-detection. We will create artificial intelligence (AI) based algorithm(s). First, we will create a logistic

regression model based on standard EEG features, e.g. time domain characteristics, power spectral density in different frequency bands, coherence measures, and entropy measures. This will be the reference to assess the improvement of the novel AI based models. Second, we will work on EEG classification algorithms based on random forests and support vector machines, using the same EEG features as input. Finally, to support future studies, we will explore new methods that use raw EEG data as input, such as convolutional or recurrent neural networks³³⁻³⁵.

STUDY PHASE 4

For phase 4 of this study, we will determine the diagnostic accuracy of several existing and one or more self-developed EEG data based algorithms for LVO-a detection by comparing the proportions of patients with and without an LVO-a as predicted by EEG to the proportion of patients with and without an LVO-a as diagnosed by the treating physician. An ROC curve will be plotted for each algorithm and the optimal cut-off value will be determined. For this cut off value, the sensitivity, specificity, negative predictive value and positive predictive value will be reported with 95% confidence intervals.

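### The rationale puts specificity first, but the primary measure is a whole-curve AUC and the phase 4 cut-off is chosen in the phase 4 data without a stated criterion, so sensitivity at high specificity gets no prespecified estimate

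*Combined protocol and SAP*

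**What the plan says.** Section 1 asks a triage method for both high sensitivity and high specificity, and then ranks them: "we deem the specificity of the method even more important". It gives two reasons. EVT hospitals are overburdened by patients who do not need them. High specificity would also make it possible, in patients with a high likelihood of LVO-a, "to minimize (or maybe even leave out) diagnostic procedures in the emergency room and to present these patients directly to the angiography room".

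The main measure is named in two ways. Section 8.1.1, like the summary, states: "The primary end point of the study is the area under the ROC curve of the theta/alpha ratio for diagnosis of LVO-a". Section 4.4 states for phase 4: "our primary outcome measure is the specificity of the dry electrode cap EEG in a population of patients with a suspected AIS". The sample size follows the second: "Sample size calculation is based on an expected specificity of 70% for LVO-a", and with 5% incidence, "an alpha of 0.05, and a maximum margin of error of 7%, 174 patients with a suspected AIS are required".

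Section 10 says for phase 4: "An ROC curve will be plotted for each algorithm and the optimal cut-off value will be determined". Sensitivity, specificity, PPV and NPV are then reported at that cut-off with 95% confidence intervals. Section 10 also determines an optimal cut-off per algorithm in phase 3, but does not say that it is carried into phase 4. Neither place defines optimal, sets a minimum specificity or names a target PPV. The protocol states no expected sensitivity.

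**The concern.** The stated priority does not reach the analysis. An AUC averages sensitivity over all specificities, including low ones of no use for triage, and gives the high-specificity end no special weight. The cut-off rule could have carried the priority, but it has no criterion.

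Specificity is not a fixed property of a continuous ratio; it follows from the threshold. Until the threshold rule is given, the quantity on which section 4.4 sizes the study is undefined. Choosing the threshold and estimating accuracy in the same phase 4 patients also tends to flatter whatever the choice optimises, the more so with few cases.

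At stake is a trial that reports a respectable AUC and one operating point chosen after the data are seen, with no planned estimate where its own rationale says the answer matters.

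**Working it through.** **Inputs.** Section 4.4: specificity (Sp) 70%, LVO-a incidence 5% (originally 7%), alpha 0.05 (taken as two-sided), margin of error 7%, 174 evaluable patients, 55% dropout, 386 recruited. Section 4.4, phase 3: about 240 patients without LVO-a. Sensitivity (Se) is not given, so it is varied or bounded.

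**1. The plan's own sample size.** N = 1.96² × Sp(1−Sp) / [d² × (1−prevalence)] = 1.96² × 0.21 / (0.0049 × 0.95) = 164.6 / 0.95 = 173.3, rounded up to 174. Dropout: 174 / 0.45 = 386.7, against 386 stated. The figures reproduce, so 70% and 5% are the working inputs, and phase 4 is sized for the precision of specificity, not for the AUC.

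**2. Expected counts.** 174 × 0.05 = 8.7, about 9 with LVO-a; 174 × 0.95 = 165.3, about 165 without.

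**3. PPV at the planning values.** PPV = Se × 0.05 / (Se × 0.05 + 0.30 × 0.95).

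| Sensitivity (assumed) | PPV | One LVO-a per | Share EEG-positive |
|---|---|---|---|
| 60% | 9.5% | 10.5 positives | 31.5% |
| 80% | 12.3% | 8.1 positives | 32.5% |
| 100% | 14.9% | 6.7 positives | 33.5% |

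PPV rises with sensitivity, so the last row is a ceiling that needs no assumption about sensitivity: 0.05 / 0.335 = 14.9%. At 7% incidence it is 0.07 / (0.07 + 0.30 × 0.93) = 20.1%, or 1 in 5.

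**4. The ceiling at higher specificity (5% incidence, Se 100%).** Sp 84%: 0.05 / (0.05 + 0.152) = 24.8%. Sp 92%: 0.05 / (0.05 + 0.076) = 39.7%.

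**5. Whether the AUC can stand in for sensitivity at high specificity.** Illustration with an assumed binormal model and AUC 0.75; r is the ratio of the SD in cases to that in non-cases. The mean difference is m = Φ⁻¹(0.75) × √(1 + r²), and sensitivity at 90% specificity is Φ((m − 1.282) / r). This gives 15%, 37% and 55% for r = 0.5, 1 and 2. Algorithms with the same AUC can differ more than threefold at that point.

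**6. What an equal-weight cut-off would do.** The plan does not say that it will use one; this shows only that the criterion matters. With equal SDs, d = √2 × Φ⁻¹(AUC) and the equal-weight point is Se = Sp = Φ(d/2).

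| AUC (assumed) | Equal-weight Se = Sp | PPV there | Se at Sp 90% | PPV there |
|---|---|---|---|---|
| 0.75 | 68% | 10% | 37% | 16% |
| 0.85 | 77% | 15% | 57% | 23% |

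**7. Precision with a fixed cut-off in phase 4.** Specificity among 165: half-width 1.96 × √(0.21/165) = 7.0 points at 70%, and 1.96 × √(0.09/165) = 4.6 points at 90%. Sensitivity among 9: 5/9 has an exact 95% CI of 21% to 86%. PPV with 7 true and 50 false positives: 12.3%, exact 95% CI 5.1% to 23.7%.

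**The case against.** For a first accuracy study of EEG in LVO-a, a threshold-free AUC is a defensible summary, and section 1 asks for both properties. The priority is not absent from the plan either: section 4.4 names specificity as the phase 4 primary outcome measure and sizes the study for its precision. An ROC curve will be plotted for every algorithm, so a high-specificity point can be read off, and a low PPV would be visible because PPV is reported. All of this is fair, and it is why the AUC should stay. It does not supply a prespecified point with an interval. A point read from the plot is chosen after the fact, and section 4.4 contradicts section 8.1.1 rather than carrying the priority through.

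A reader might go further in four ways that the documents do not support.

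- That the cut-off will weight sensitivity and specificity equally. Section 10 leaves the criterion open; it does not name an equal-weight one.
- That 1 in 8 EEG-positive patients will have an LVO-a. This needs a sensitivity of about 81%, which the plan does not give. The supportable statement is at most 1 in 6.7.
- That the trial will operate at 70% specificity. That figure is a planning input for precision, not a chosen operating point.
- That the results cannot support direct presentation to the angiography room. That use is a hedged future prospect in the rationale, not a study objective; the objective is diagnostic accuracy, and the main use described is choice of hospital. Nor do the documents set a PPV that such a use would require.

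**Conclusion.** The point holds in a limited form. The plan ranks specificity first, contradicts itself on whether specificity or the AUC is the primary measure, and leaves the phase 4 cut-off without a criterion. Followed as written, it gives no prespecified estimate of sensitivity at high specificity, and its estimates at a cut-off chosen in the same data with about 9 LVO-a cases will tend to be optimistic. The amount of optimism cannot be computed, because it depends on the unstated criterion.

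At 70% specificity and 5% incidence, at least 85% of EEG-positive patients would have no LVO-a whatever the sensitivity (at least 80% at 7% incidence). Results near that point would not identify the high-likelihood group that section 1 has in mind. This bound uses only the plan's own inputs. The comparisons of AUC with sensitivity at 90% specificity rest on an assumed binormal model and assumed AUCs, and serve as illustration only.

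**What to change.** 1. Reconcile section 4.4 with section 8.1.1 and the summary on which measure is primary. The AUC can stay.
2. In section 10, replace the optimal cut-off by one cut-off per algorithm, fixed in phase 3 at a prespecified high specificity that the sponsor justifies for the intended use. The 84-92% in section 1 comes from EEG monitoring in carotid surgery and can serve only as an illustration. A rule that takes the highest sensitivity among cut-offs with specificity of at least 70% would not do: sensitivity falls as specificity rises, so it always settles near 70%. In the equal-SD model at AUC 0.85 it would lower specificity from 77% to 70% and PPV from 14.9% to 12.7%.
3. Apply the locked cut-off unchanged in phase 4. Report specificity, sensitivity, PPV, NPV and the share EEG-positive with exact 95% CIs, plus a partial AUC over the high-specificity range. Label any cut-off re-optimised in phase 4 as exploratory.
4. State in section 4.4 that 70% specificity at 5% incidence caps PPV at 14.9%.

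The cost is wording and a few more results columns; no added patients or procedures. There are three downsides. Sensitivity at the high-specificity point will usually be lower than at an equal-weight cut-off. With about 9 cases it will be very imprecise, and the report should say so. And a cut-off set in the emergency room may not give the same specificity in the ambulance. Even with all 240 phase 3 patients without LVO-a, a 90% target carries a half-width of 1.96 × √(0.09/240) = 3.8 points, so the specificity achieved in phase 4 must be reported next to the target.
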